**6.7 Assessment of Safety**

Any patient who receives treatment on this protocol will be evaluable for toxicity. Each patient will be assessed periodically for the development of any toxicity according to the Time and Events tables. Toxicity will be assessed according to the NCI CTCAE v5.0.

**6.8 Evaluation of Response by irRECIST [62] per Bohnsack et al.**

**New measurable lesions in irRECIST:**

New measurable lesions will not necessarily constitute PD or preclude partial response (PR). Rather, the difference between the current size of a measurable

lesions and its size prior to meeting criteria for measurability will be added to the sum of tumor measurements.

**Definition of Response Using irRECIST**

**irComplete Response (irCR):** Complete disappearance of all lesions (whether measurable or not) and no new lesions. Lymph nodes must decrease to <10mm in short axis. Confirmation of a response is not mandatory. It is the judgment of the investigator whether a nonmeasurable radiographic nodule is likely cancerous; only nodules felt likely cancerous will preclude the judgement of irCR.

- **irPartial Response (irPR):** Decrease in tumor burden  $\geq 30\%$ , in total measured tumor burden relative to baseline, non-target lesions are irNN, and no unequivocal progression of new non-measurable lesions
- **irNon CR/Non-PD (irNN):** No target disease was identified at baseline and at follow up the patient fails to meet criteria for irCR or irPD.
- **irStable Disease (irSD):** Does not meet criteria for irCR or irPR, in the absence of irPD.
- **irProgressive Disease (irPD):** At least 20% and minimum 5 mm absolute increase in total measured tumor burden compared to nadir, or irPD for non-target or new on-measurable lesions. Confirmation of progression is recommended minimum of 4 weeks after the first irPD assessment.
- **Nonprogressive disease:** Measurable disease is not required for this study. Patients with CR at the time of study entry or otherwise nonmeasurable disease will be assessed for progression. In the event of PD, this should be noted. In the absence of meeting criteria for progression, nonprogressive disease should be coded (NPD).

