### 2.4.2 Secondary Endpoints

**2.4.2.1 Median PFS.** PFS will be defined as the time from D1 of treatment until death or progression.

**2.4.2.2 Median OS.** OS is defined as the time from D1 of treatment to death from any cause.

**2.4.2.3 Tumor response** will be defined as the proportion of patients with reduction in tumor (irCR+irPR) per irRECIST criteria outlined in section 6.8.

**2.4.2.4 Clinician assessed toxicity** will be classified and graded according to the National Cancer Institute's Common Terminology Criteria for Adverse Events (NCI-CTCAE, version 5.0).

**2.4.2.5 Use of modified Borg rating scale** for perceived dyspnea (10 point scale from 1 to 10 which measures perception of dyspnea) [59, 60] (Provided in 11.6 **Appendix F: Borg Scale**).

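### Section 6.8 defines partial response inconsistently: irPR depends on irNN, which is defined only for patients without target disease and leaves out non-target disease that has disappeared

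*Combined protocol and SAP*

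**What the plan says.** Section 2.4.2.3 makes tumor response a secondary endpoint, "will be defined as the proportion of patients with reduction in tumor (irCR+irPR) per irRECIST criteria outlined in section 6.8". The wording of section 6.8 is therefore the working definition.

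Section 6.8 sets these rules:

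- **irCR:** "Complete disappearance of all lesions (whether measurable or not) and no new lesions".
- **irPR:** a fall of at least 30% in measured burden from baseline, with two further conditions: "non-target lesions are irNN, and no unequivocal progression of new non-measurable lesions".
- **irNN** (labelled as non-CR/non-PD): "No target disease was identified at baseline and at follow up the patient fails to meet criteria for irCR or irPD".
- **irSD**, the residual category: "Does not meet criteria for irCR or irPR, in the absence of irPD".

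The section adds "Measurable disease is not required for this study" and gives a separate code, NPD, to patients without measurable disease who have not progressed. Section 8.3 plans only to report response rates; it gives no assumed rate, test or power for them.

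**The concern.** irPR uses irNN as a condition on a set of lesions, while the bullet after it defines irNN as a state of the whole patient, and only of a patient with no target disease. The two bullets cannot both apply to a patient who has target and non-target lesions. The irPR bullet also does not mention non-target lesions that have gone completely, although that is a better result than the persistence it asks for.

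At stake is the irCR+irPR rate. A patient wrongly refused irPR is reported as stable disease. Two assessors who follow the same text could also classify the same scan differently.

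**Working it through.** The documents state no response rate and no distribution of lesion types, so there is no figure to reproduce. The check is to apply the definitions to each combination of target and non-target status, assuming no progression and no new lesions.

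**Three versions of the non-target condition in irPR**

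- *Literal:* irNN as defined, so it is never met by a patient who had target disease at baseline.
- *Label:* irNN taken as a lesion-level status, neither complete response nor progression.
- *Repaired:* non-target lesions absent at baseline, all disappeared, or persisting without unequivocal progression.

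Where there were no non-target lesions at baseline, the condition is taken as met in all three versions, because it has nothing to act on. The text does not say this, so it is an assumption.

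| Target lesions | Non-target lesions | Literal | Label | Repaired |
|---|---|---|---|---|
| Partial response | None at baseline | irPR | irPR | irPR |
| Partial response | Persist, no progression | **irSD** | irPR | irPR |
| Partial response | All disappeared | **irSD** | **irSD** | irPR |
| All disappeared | Persist, no progression | **irSD** | irPR | irPR |
| All disappeared | None, or all disappeared | irCR | irCR | irCR |
| Stable | None, all disappeared, or persist | irSD | irSD | irSD |
| None at baseline | Persist, no progression | irNN | irNN | irNN |
| None at baseline | All disappeared | irCR | irCR | irCR |

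**What the table shows**

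1. *Literal.* irPR needs a fall from a measured baseline, so target disease must have been present. irNN needs target disease to have been absent. With non-target lesions also present, the conditions exclude each other and three rows fall to irSD. Only a patient with target disease alone reaches irPR.
2. *Label.* One row is lost: target partial response with all non-target disease gone. That patient is irSD, while the patient with the same target response and persisting non-target disease is irPR. The better outcome receives the worse code.
3. *Direction.* Every cell that differs from the repaired column moves from irPR to irSD and none moves the other way, so irCR+irPR can only fall. The irCR rows are identical in all columns.
4. *Scale.* Section 8.2 plans 24 patients, and section 8.1 includes everyone treated at dose level 2 in the efficacy analysis. If all 24 form the denominator, one reclassified patient changes the rate by 1/24 = 4.2 percentage points. The documents do not allow a count of how many patients would be reclassified.

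**The case against.** The strongest reply is that nobody would apply the literal text. The label says non-CR/non-PD, the same section speaks of irPD for non-target lesions, and it cites a published source for the criteria. An assessor would probably award irPR when non-target lesions persist without progressing. This is fair, and it makes the label reading the more plausible one. It does not remove the problem, because complete disappearance of non-target lesions is still missing from irPR on that reading. The section also defines best overall response (irBOR) as the best observed. If the reported rate uses it, a patient scored irPR on the label reading before the non-target disease clears would keep that code, so the loss could be smaller still. Section 2.4.2.3 does not say whether irBOR is used.

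Four stronger conclusions are tempting, and the documents do not support them.

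- *That irPR is unreachable.* Patients with target disease only can reach it on either reading. It would be closed to everyone only on the literal reading, and only if every patient had recorded non-target disease.
- *That patients whose effusion clears lose irPR.* Every patient enters with a confirmed malignant effusion (section 3.1.5), but nothing says it is scored as a non-target lesion. Nor is clearance by the primary endpoint (drainage of 50 cc or less on three consecutive occasions, with symptom improvement) the same as disappearance on imaging. On the label reading irPR is lost only if all non-target disease has gone, and in stage IV disease other lesions may remain.
- *That the understatement can be quantified.* The 45% and 70% in section 8.2 are hypothesised rates of effusion resolution, not rates of lesion disappearance, and no target-lesion response rate is given.
- *That the correlative analyses inherit the error.* Sections 1.8 and 2.3 refer to response without tying it to irCR+irPR.

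**Conclusion.** The inconsistency is real and lies within two adjacent bullets of section 6.8. As written, no patient with both target and non-target disease can be irPR. On the more charitable reading, a patient with target partial response and complete disappearance of non-target disease is coded below one whose non-target disease persists. Any resulting misclassification biases irCR+irPR downward. The amount is unknown, and it is zero if assessors in practice accept both disappearance and non-progressing persistence. A reader should therefore not conclude that the reported rate will be understated, only that the text permits it.

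The consequence is limited: this is a secondary endpoint reported descriptively, and the drainage-based primary endpoint does not use section 6.8. Whether effusion clearance matters for tumor response depends on how the effusion is scored, which the plan leaves open. The definition should still be corrected, because otherwise a named endpoint depends on assessors setting the written rule aside.

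**What to change.** Edit section 6.8 as follows:

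1. **irPR:** at least a 30% decrease in total measured burden from baseline, with non-target lesions absent at baseline, completely disappeared, or persisting without unequivocal progression. Keep the existing condition on new non-measurable lesions.
2. **Non-target status:** define a lesion-level non-CR/non-PD status, meaning that one or more non-target lesions persist without unequivocal progression. Keep patient-level irNN only for patients without target disease, and reconcile it with the NPD code, which overlaps it. Do not use irCR for the disappearance of non-target lesions alone, since irCR is a patient-level term requiring all lesions to be gone.
3. **Effusion:** state whether the pleural effusion is scored as a non-target lesion.

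The cost is a few lines of text, with no new data, visits or change in sample size. If any responses have already been assessed, they should be re-read against the revised wording.

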**Immune-related Best Overall Response (irBOR):**

IrBOR is the best response observed during the relevant time period. Of note, when total tumor burden increases and the patient is maintained on therapy, and tumor then shrinks (pseudo-progression) the second measurement will be utilized.

**Designation of pseudo-progression:**

The phenomenon of pseudo-progression is of particular interest in this trial. For the purpose of this trial, pseudo-progression will be defined as any  $\geq 10\%$  increase in tumor burden followed by a  $\geq 10\%$  decrease in tumor burden prior to change in therapy. Such occurrences will be noted for the purpose of exploratory hypothesis-generating analyses.

## 7.0 ADVERSE EVENTS

### 7.1 Definitions

#### 7.1.1 Adverse Event (AE)

An adverse event (AE) is any untoward medical occurrence (e.g., an abnormal laboratory finding, symptom, or disease temporally associated with the use of a drug) in a patient or clinical investigation subject administered a pharmaceutical product and which does not necessarily have a causal relationship with this treatment. An AE can therefore be any unfavorable and unintended sign (including an abnormal laboratory finding), symptom, or disease temporally associated with the use of a medicinal product, whether or not related to the medicinal product.

Hospitalization for elective surgery or routine clinical procedures that are not the result of an AE (e.g., surgical insertion of central line) need not be considered AEs and should not be recorded as an AE. Disease progression should not be recorded as an AE, unless it is attributable by the investigator to the study therapy.

From the time of treatment through 30 days following cessation of treatment, all adverse events must be reported by the investigator. Such events will be recorded at each examination on the Adverse Event case report forms/worksheets. The reporting timeframe for adverse events meeting any serious criteria is described in section 7.3. The investigator will make every attempt to follow all subjects with non-serious adverse events for outcome.

#### 7.1.2 Suspected Adverse Reaction (SAR)

A suspected adverse reaction (SAR) is any AE for which there is a *reasonable possibility* that the drug is the cause. *Reasonable possibility* means that there is evidence to suggest a causal relationship between the drug and the AE. A suspected adverse reaction implies a lesser degree of certainty about causality than adverse reaction, which means any adverse event caused by a drug.

Causality assessment to a study drug is a medical judgment made in consideration of the following factors: temporal relationship of the AE to study drug exposure, known mechanism of action or side effect profile of study treatment, other recent or concomitant drug exposures, normal clinical course of the disease under investigation, and any other underlying or concurrent medical conditions. Other factors to consider in considering drug as the cause of the AE:

- Single occurrence of an uncommon event known to be strongly associated with drug exposure (e.g., angioedema, hepatic injury, Stevens-Johnson Syndrome)
- One or more occurrences of an event not commonly associated with drug exposure, but otherwise uncommon in the population (e.g., tendon rupture); often more than once occurrence from one or multiple studies would be

needed before the sponsor could determine that there is *reasonable possibility* that the drug caused the event.

- An aggregate analysis of specific events observed in a clinical trial that indicates the events occur more frequently in the drug treatment group than in a concurrent or historical control group

### 7.1.3 Unexpected AE or SAR

An AE or SAR is considered unexpected if the specificity or severity of it is not consistent with the applicable product information (e.g., Investigator's Brochure (IB) for an unapproved investigational product or package insert/summary of product characteristics for an approved product). Unexpected also refers to AEs or SARs that are mentioned in the IB as occurring with a class of drugs or as anticipated from the pharmacological properties of the drug, but are not specifically mentioned as occurring with the particular drug under investigation.

### 7.1.4 Serious AE or SAR

An AE or SAR is considered serious if, in the view of either the investigator or sponsor, it results in any of the following outcomes:

- Death;
- Is life-threatening (places the subject at immediate risk of death from the event as it occurred);
- Requires inpatient hospitalization (>24 hours) or prolongation of existing hospitalization;\*
- Results in congenital anomaly/birth defect;
- Results in a persistent or significant incapacity or substantial disruption of the ability to conduct normal life functions;
- Important medical events that may not result in death, be life-threatening, or require hospitalization may be considered a serious adverse drug experience when, based upon appropriate medical judgment, they may jeopardize the patient or subject and may require medical or surgical intervention to prevent one of the outcomes listed in the definition. For reporting purposes, also consider the occurrences of pregnancy as an event which must be reported as an important medical event.
- Potential drug induced liver injury (DILI) is also considered an important medical event.
- Suspected transmission of an infectious agent (e.g., pathogenic or nonpathogenic) via the study drug is an SAE.
- Although pregnancy, overdose, and cancer are not always serious by regulatory definition, these events must be handled as SAEs.

\*Hospitalization for anticipated or protocol specified procedures such as administration of chemotherapy, central line insertion, metastasis interventional

therapy, resection of primary tumor, or elective surgery, will not be considered serious adverse events.

Pregnancy that occurs during the study must also be reported as an SAE.

**Note:** In addition to the above criteria, adverse events meeting either of the below criteria, although not serious per ICH definition, are reportable to the BMS and Amgen in the same timeframe as SAEs to meet certain local requirements. Therefore, these events are considered serious by BMS for collection purposes.

- Is a new cancer (that is not a condition of the study);
- Is associated with an overdose.

## 7.2 Documentation of non-serious AEs or SARs

For non-serious AEs or SARs, documentation must begin from day 1 of study treatment and continue through the 100 day follow-up period after nivolumab treatment is discontinued. Subjects should be followed for AEs for at least 30 days after talimogene laherparepvec is discontinued.

Collected information should be recorded in the Case Report Forms (CRF) for that patient. Please include a description of the event, its severity or toxicity grade, onset and resolved dates (if applicable), and the relationship to the study drug.

## 7.3 SAEs or Serious SARs

### 7.3.1 Timing

After informed consent but prior to initiation of study medications, only SAEs caused by a protocol-mandated intervention will be collected (e.g., SAEs related to invasive procedures such as biopsies, medication washout).

For any other experience or condition that meets the definition of an SAE or a serious SAR, recording of the event must begin from day 1 of study treatment and continue at least through the 100 day follow-up period after treatment is discontinued. Ultimately, the event should be followed until resolution of symptoms or the investigator determines that symptoms have improved to the fullest extent possible.

### 7.3.2 Documentation and Notification

SAEs or Serious SARs must be recorded in the SAE console within Oncore™ for that patient within 24 hours of learning of its occurrence.

### 7.3.3 Reporting

#### 7.3.3.1 IRB Reporting Requirements:

The UNC-IRB will be notified of all SAEs that qualify as an Unanticipated Problem as per the UNC IRB Policies using the IRB's web-based reporting

system (see section 9.5.3) within 7 days of the Investigator becoming aware of the problem.

### **7.3.3.2 Pregnancy**

Although pregnancy and lactation are not considered adverse events, it is the responsibility of investigators or their designees to report any pregnancy or lactation in a subject (spontaneously reported to them) that occurs during the trial.

Pregnancies and lactations that occur after the consent form is signed but before treatment allocation/randomization must be reported by the investigator if they cause the subject to be excluded from the trial, or are the result of a protocol-specified intervention, including but not limited to washout or discontinuation of usual therapy, diet, placebo treatment or a procedure.

Pregnancies and suspected pregnancies (including a positive pregnancy test regardless of age or disease state) of a female subject occurring while the subject is on study or within 30 days of the subject's last dose of talimogene laherparepvec or within the period stipulated for continued contraceptive use for WOCBP (5 months) and sexually active men (7 months) after the subject's last dose of nivolumab should be recorded as SAEs. The patient is to be discontinued immediately from the study for a pregnancy event.

The Investigator will follow the female subject until completion of the pregnancy, and must document the outcome of the pregnancy (either normal or abnormal outcome) and report the condition of the fetus or newborn to the UNC study coordinator. If the outcome of the pregnancy was abnormal (e.g., spontaneous or therapeutic abortion), the Investigator should report the abnormal outcome as an AE. If the abnormal outcome meets any of the serious criteria, it must be reported as an SAE.

### **7.3.3.3 Laboratory Test Abnormalities**

The following laboratory abnormalities should be documented and reported appropriately as AEs:

- any laboratory test result that is clinically significant or meets the definition of an SAE
- any laboratory abnormality that required the subject to have study drug discontinued or interrupted
- any laboratory abnormality that required the subject to receive specific corrective therapy.

### **7.3.3.4 Overdose**

An overdose is defined as the accidental or intentional administration of any dose of a product that is considered both excessive and medically important. All occurrences of overdose must be reported as an SAE.

### 7.3.3.5 Other Safety Considerations

Any significant worsening noted during interim or final physical examinations, electrocardiograms, x rays, and any other potential safety assessments, whether or not these procedures are required by the protocol, should also be recorded as a non-serious or serious AE, as appropriate, and reported accordingly.

### 7.3.3.6 Amgen Reporting Requirements:

Please refer to the table below regarding policy for reporting SUSARs, and other safety related data to Amgen.

#### Expedited Reporting Requirements for Interventional Studies

Safety Data	Timeframe for Submission to Amgen
Suspected Unexpected Serious Adverse Reaction (SUSARs)	Individual reports sent to Amgen at time of expedited reporting to the IRB and/or FDA
Serious Adverse Events (SAEs) (related)	Individual reports sent to Amgen at time of expedited reporting to IRB and/or FDA
Pregnancy/Lactation	Individual reports sent within 10 days of Sponsor/Investigator awareness (Use Amgen template forms provided for the study to report pregnancy or lactation events).

Individual reports should be faxed to [name] or scanned and sent via email to [[contact]](mailto:[contact]).

Aggregate reports should be submitted via email to the non-Amgen sponsored Clinical Research (NASCR) manager accompanied by the Aggregate Safety Reporting fax transmittal form for Investigator Sponsored Studies provided for the study.

Please refer to the ICH Guidelines E2A for safety related definitions and terminology:

[http://www.ich.org/fileadmin/Public\\_Web\\_Site/ICH\\_Products/Guidelines/Efficacy/E2A/Step4/E2A\\_Guideline.pdf](http://www.ich.org/fileadmin/Public_Web_Site/ICH_Products/Guidelines/Efficacy/E2A/Step4/E2A_Guideline.pdf)

### 7.3.3.7 Suspected Herpetic Events

**Suspected herpetic events must be reported to Amgen within 24 hours of awareness.** Reporting is required for: (1) suspected herpetic events in treated patients; (2) suspected herpetic events in at risk health care professionals with direct or indirect exposure and 3) suspected herpetic events in treated patient's close contacts.

In addition to reporting these events, suspected herpetic lesions should be swabbed and submitted for quantitative polymerase chain reaction testing for the detection of talimogene laherparepvec. Samples should be collected using appropriate technique and a flocced swab from site supplies. This test is likely to

be more reliable if performed within **the first three days of symptom appearance**. Amgen does not require quantitative polymerase chain reaction or other testing for wild type herpes simplex virus-1. See section below on reporting process for health care providers which should be followed if herpetic lesions are suspected.

Reporting Process for Treated Patients:

- Any suspected herpetic lesion should be reported to Amgen at [name] or [name], evaluated by the sponsor/investigator and swabbed for quantitative polymerase chain reaction testing
- Once an initial report has been made, additional materials will be provided, including reporting forms and supplies needed for shipment of swab samples. Amgen will require patient consent for quantitative polymerase chain reaction testing, which must be obtained prior to swabbing.

Reporting process for health care providers and close contacts:

- Sponsor investigator should advise any health care providers and/or close contacts with suspected herpetic lesions to contact their personal physician to facilitate reporting to Amgen. Suspected herpetic lesions should be reported by the personal physician or exposed individual to Amgen at [name]. Once an initial report has been made, additional materials will be provided, including reporting forms and supplies needed for shipment of swab samples. Amgen will require patient consent for quantitative polymerase chain reaction testing, which must be obtained prior to swabbing.

